Rationale: In order to preserve the residual hearing in patients with sensorineural hearing loss (SNHL) receiving a cochlear implant (CI), the insertion trauma to the delicate and microscopic structures of the cochlea needs to be minimized. The surgical procedure starts with the conventional mastoidectomy-posterior tympanotomy (MPT) approach to the middle ear, and is followed by accessing the cochlea, with either a cochleostomy (CO) or via the round window (RW). Both techniques have their benefits and disadvantages. Another aspect is the design of the electrode array. There are fundamentally two different designs: a 'straight' lateral wall lying electrode array (LW), or a 'pre-curved' perimodiolar cochlear lying electrode array (PM). Interestingly, until now, the best surgical approach and type of implant is unknown. Our hypothesis is that the combination of a RW approach and a LW lying electrode array minimizes insertion trauma, leading to better hearing outcome for SNHL patients.

Objective: Comparison of hearing preservation and outcome of two fundamentally different cochlear implants designs (LW or PM) and the two most used surgical approaches (RW or CO). Secondly, asses the structure preservation (i.e., scalar position) of each combination of electrode design/surgical approach. Thirdly, find objective electrophysiological measures for insertion trauma.

Study population: A total of 48 patients with severe SNHL, age ≥ 18 years, who meet the in/exclusion criteria used for cochlear implantation.

Study design: Randomized controlled single-blind trial consisting of four groups: 1: RW and LW, 2: CO and LW, 3: RW and PM and 4: CO and PM.

Intervention: Randomization to one of the four groups.

Main study parameters/endpoints: Primary outcome: Pre- and postoperative hearing thresholds of (low frequency) pure tone audiometry (LF-PTA), secondary outcomes: scalar position of the electrode array, ECochG measures and speech perception score.

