Figure 1: This is a schematic coronal plane of a cochlear duct. The cochlea consist of several compartments: scala vestibuli, scala media and scala tympani. The CI should reside in the scala tympani, herein laterally and medially for the LW and PM electrode array respectively. Translocation of the CI from scala tympani to the scala media or scala vestibuli (from downward to upward) damages vital structures like the basilar membrane with the organ of Corti or stria vascularis.

[figure not shown]

Figure 2: Cone beam CT scan. 'Cochlear view': position of the CI (the white dotted radiopaque curled line) can be easily assessed. The 16 electrodes of the CI are reflected by the white dots.

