2. OBJECTIVES

Primary Objective:

To compare hearing preservation percentage after cochlear implantation between two surgical approaches (CO, RW) and two electrode array designs (LW, PM).

Secondary Objective(s):

- To determine the relationship of scalar position of the electrode array and hearing preservation (i.e. residual acoustic hearing).
- To determine the relationship of scalar position of the electrode array and hearing performance after one year with CI.
- To assess residual hearing over time after implantation.
- To find which ECochG measures can be used best for assessment of insertion trauma.
- To determine the relationship between ECochG measures and residual hearing and speech perception postoperatively.
- To determine the relationship between ECochG measures and scalar position of the electrode array.

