4.4 Sample size calculation

Hearing preservation is the main outcome variable (see further 5.1). Based on literature (Manjaly et al., 2018; Rader et al., 2018; Sierra et al., 2019) we expect a large range of hearing preservation for each group, from 0 (no preservation, i.e., loss of all hearing) to 100 (full preservation, hearing stable), and occasionally above (improved hearing). The three studies showed means of 56, 74, and 53, respectively and within-group standard deviations, σ_w , of 37, 19 and 37. Weighing the larger studies more (Manjaly, Sierra) we estimate $\sigma_w = 35$ group means of 50 with clinically interesting differences of 40 between best and worst group means. This yields a variance between groups of 400, i.e., $\sigma_B = \sqrt{400} = 20$ (σ_B : standard deviation between groups). Thus, effect size $\sigma_B / \sigma_w = 0.57$. Using a group size of 12 yields a robust power of 0.9. We used G*power (version 3.1.9) to calculate the power based on effect size and sample size with a one-way ANOVA test, with fixed effects.

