We will use the cone beam CT scanner to postoperatively assess the scalar location of the electrode array for all four groups. The CB-CT has been proven to be the best imaging modality for assessing the scalar location postoperatively, as it has low radiation artefacts (caused by the metal parts of the cochlear implant) and high spatial resolution needed to image the cochlea and its internal parts. In addition, it has relatively low radiation exposure, is less likely to trigger claustrophobic reactions and requires shorter scanning durations compared to traditional CT scanners (Li, 2013, Nardi et al., 2018, Casselman et al., 2013).

We will assess CI translocation by making multiplanar midmodiolar reconstructions of the cone beam CT images, which is validated by numerous papers (Mosnier et al., 2017, Zou et al., 2015, Saeed et al., 2014). These multiplanar reconstructions will allow us to systematically indicate for every stimulation point of the cochlear implant the exact scalar position (i.e. scala tympani or scala vestibuli). The main researcher and an experienced otologist will analyse the CT scans blindly for each patient.

3. ECochG

'Electrocochleography' (ECochG) is a method for recording the electrical potentials of the cochlea. The ECochG is composed of several components: the compound action potential (CAP), cochlear microphonics (CM) and the summating potential (SP). In essence, the CAP is generated by the auditory nerve activity, the CM and SP are generated by the hair cells of the

organ of Corti. The CM is an AC response following the tone, and the SP is a DC response. Outcome measures include the CM amplitude and the total ECochG amplitude. Potentially, the difference in the amplitude of the total ECochG response after and before insertion might contain information about insertion trauma, i.e. damage to the basilar membrane, stria vascularis or other structures.

We will use the most apical contact point of the electrode array to measure these outcomes. The acoustic pure tones and click stimuli will be delivered via the insert earphone. This will be coupled to the measurement equipment that is provided with the CI by the manufacturer. The amplifier in the implant will be used for amplification of the response.

4. Speech perception scores

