7. STATISTICAL ANALYSIS

7.1 Descriptive statistics

We will use an ANOVA test to compare the primary outcome measure hearing preservation (see 5.3) between the four groups. We will do the same for the CVC word score tests (with and without noise) between the groups.

Fisher's exact test of independence will be used to compare the electrode location within the scala tympani (correct location after insertion) between CO or RW approach, and between PM or LW electrode insertion.

We will also use multiple regression analysis to identify independent predictors of hearing preservation. Among the factors to examine are insertion depth and cochlear volume.

We will use a Pearson correlation test to examine the correlations between the ECochG responses and hearing preservation at the various time points (during and after cochlear implantation)..

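### The Pearson test of ECochG against hearing preservation names no adjustment for the randomised array or approach, so an array difference could create or hide an association; an arm-adjusted estimate should be reported beside it.

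*Protocol*

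**What the plan says.** Protocol section 7.1 fixes the method: "We will use a Pearson correlation test to examine the correlations between the ECochG responses and hearing preservation at the various time points". Neither array, approach nor randomised group is mentioned. The analysis serves two secondary objectives in section 2: finding the ECochG measures best suited to assess insertion trauma, and "To determine the relationship between ECochG measures and residual hearing and speech perception postoperatively".

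Three other places bear on it.

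- **Recording site.** Section 5.3, under ECochG: "We will use the most apical contact point of the electrode array to measure these outcomes". The Figure 1 legend in section 1 says the implant should lie in the scala tympani, "herein laterally and medially for the LW and PM electrode array respectively".
- **Expected direction.** The Summary: "Our hypothesis is that the combination of a RW approach and a LW lying electrode array minimizes insertion trauma, leading to better hearing outcome".
- **Size used for planning.** Section 4.4 takes a within-group SD of 35, 12 patients per group, and "clinically interesting differences of 40 between best and worst group means".

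Section 7.1 also plans a multiple regression for independent predictors of hearing preservation. It gives insertion depth and cochlear volume as examples and names neither ECochG nor the randomised group.

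**The concern.** The randomised array may act on both variables being correlated. It fixes where the recording contact lies, so ECochG amplitude may differ between LW and PM recipients with no difference in trauma. It is also one of the two factors hypothesised to affect preservation. A correlation over all 48 patients that ignores the groups mixes two things: whether, among patients treated alike, a better ECochG response goes with better preservation; and whether the array with the larger mean amplitude happens to have the better or worse mean preservation.

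If the array shifts both in the same direction, the test can be significant when ECochG says nothing about an individual patient. If it shifts them in opposite directions, a real relation can be lost. Since one objective is to choose the best ECochG measure of trauma, the choice could fall on the measure most sensitive to array position.

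**Working it through.** **Inputs from the protocol.** Four groups of 12 (N = 48), within-group SD of preservation 35, 40 points between best and worst group means (section 4.4), equal allocation (section 5.2).

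**Assumptions.** Two-sided 5% level (the protocol states none); an LW/PM amplitude offset of d within-group SDs, with d = 0.5 or 1; a true within-group correlation ρ of 0 or 0.5.

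**The plan's own figure.** Effect size 20/35 = 0.57; the noncentral F calculation with four groups of 12 gives power 0.903 against the stated 0.9, so it reproduces. The stated between-group variance of 400 with a 40-point range requires two groups at each extreme. Section 4.4 does not say which two, so the patterns below have to be compared.

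**Expected plain correlation.** Let a be half the LW minus PM difference in mean preservation and V the between-group variance. Then approximately

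r = (35ρ + a·d/2) / √[(1225 + V)(1 + d²/4)],

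with d negative when the offset opposes the true relation. In the order RW+LW, CO+LW, RW+PM, CO+PM:

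- Array only (70, 70, 30, 30): a = 20, V = 400.
- Additive (70, 50, 50, 30): a = 10, V = (400 + 0 + 0 + 400)/4 = 200.
- Approach only (70, 30, 70, 30): a = 0, V = 400.

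No relation within groups (ρ = 0):

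- Array only, d = 0.5: 5/(40.31 × 1.031) = 0.12.
- Array only, d = 1: 10/(40.31 × 1.118) = 0.22.
- Additive, d = 0.5: 2.5/(37.75 × 1.031) = 0.06.
- Additive, d = 1: 5/(37.75 × 1.118) = 0.12.
- Approach only, or no difference: a = 0, so r = 0.

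True relation (ρ = 0.5, 35ρ = 17.5) with an opposing offset:

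- Array only: 12.5/41.55 = 0.30 and 7.5/45.07 = 0.17.
- Additive: 15/38.91 = 0.39 and 12.5/42.20 = 0.30.

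With 48 patients, significance needs |r| above 0.285.

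**Simulated rejection rates**, plain Pearson (46 df) against correlation of within-group residuals (43 df):

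| Preservation pattern | Plain, ρ = 0, d = 0.5 / 1 | Plain, ρ = 0.5, opposing d = 0.5 / 1 |
|---|---|---|
| Array only | 13% / 34% | 55% / 17% |
| Additive | 7% / 12% | 79% / 53% |
| Approach only, or none | about 5% | not the main case |

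The group-adjusted test rejects in about 5% of trials when ρ = 0 and about 95% when ρ = 0.5, whatever the pattern or offset.

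A spurious correlation needs an array difference in both variables. Loss of power needs only one: at ρ = 0.45 with no preservation difference, a 1.5 SD offset lowers plain power from 0.91 to 0.72.

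**The reverse case.** Suppose there is no positional offset and ECochG tracks preservation equally between and within groups (means 70, 70, 30, 30). Then the plain test is the stronger: 67% against 52% at r = 0.3, and 91% against 79% at r = 0.4.

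**The case against.** **The protocol does not say the correlation is pooled.** That is inferred from one named test with no mention of group. A statistical analysis plan, not at hand, could add the adjustment. This stands as a limit, but the test the protocol does name is unadjusted, and a plan following it literally would leave it so.

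**A regression is already planned.** Its list of factors is open, so ECochG with array and approach could fit inside it. That is possible but not secured, since it names neither.

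**The offset and its setting are assumed.** No LW/PM amplitude difference appears in the protocol. A reader might take 34% as the expected error rate; it requires a 1 SD offset and the whole 40 points falling between arrays. Section 4.4 gives 40 as a difference of clinical interest for the power calculation, not a forecast, and section 1 says no evidence shows one array design outperforming the other. This stands, and is why a range is shown.

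**Between-group association may be signal.** Array and approach are the trial's hypothesised causes of insertion trauma. If ECochG tracks trauma, part of the association across groups is what the objective seeks. A reader might infer that the Pearson test is invalid and should be replaced outright. The protocol does not support that: its objective asks for the relationship between ECochG and residual hearing and does not confine it to patients treated alike. This is the strongest objection, and it shapes the fix.

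**Conclusion.** The point holds as a cheap improvement to a secondary analysis. Section 7.1 names a correlation that cannot separate an array-position effect from a trauma relation, in a design that ties recording position to the randomised array. How much this matters is unknown in advance: from nothing (no array difference in amplitude or in preservation) to a spurious significance rate of 34%, or power of 17% instead of about 95%, at the unfavourable end of the offsets assumed here.

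Three stronger readings are not supported. Recording position does not differ across all four groups; it follows the array and has two levels. The adjusted test does not recover a within-patient relation; it compares patients within the same group. And the point does not extend to ECochG against speech score or scalar position, because section 7.1 assigns no Pearson test to either. The primary ANOVA is untouched.

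**What to change.** In section 7.1, keep the Pearson correlation and add a partial correlation, or a regression of preservation on ECochG, adjusted for allocated array and approach (with their interaction, that is, the four groups). Report the two side by side and base the choice of the best ECochG trauma measure on both. Agreement supports a relation not due to array position alone; disagreement shows that the array or approach matters and has to be interpreted.

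The cost is a line of text and three degrees of freedom (46 to 43). No new data are needed, since allocation is recorded. The real downside is the lower power of the adjusted test when ECochG tracks preservation equally between and within groups (52% against 67% at r = 0.3), which is the reason to add it and not to substitute it.

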Considering the surgical approach and electrode array design, it is important to note that during insertion no reliable feedback is provided, regarding the array tip position in relation to the intracochlear structures. After inserting the tip of the electrode array in the round window perforation or cochleostomy, only tactile feedback is available, which might not be sufficient to know whether the implant is correctly inserted. Correct insertion, for both cochleostomy and round window approach, ensures that the implant is in the scala tympani of the cochlea. If during insertion, the CI translocates to the scala vestibuli or scala media, the basilar membrane with the organ of Corti (the actual hearing receptor organ) is damaged (see **fig. 1**). Scalar translocation negatively influences the final hearing outcome and hearing preservation for CI patients (Holden et al., 2013, Shaul et al., 2018).

One of the possibilities to view the intracochlear structures and thereby asses the scalar location of the CI (thus providing postoperative feedback), is by applying imaging techniques after surgery such as cone beam computed tomography (CB-CT) (see **fig. 2**), which has been proven to be suitable in detecting the scalar position of the electrode array (Zou et al., 2015, Saeed et al., 2014, Mosnier et al., 2017). Another possibility to detect insertion trauma is the intraoperative, intracochlear electrocochleography (ECochG) which measures responses of residual functioning hair cells to acoustic tone stimuli. During insertion, ECochG measures can be used to assess insertion trauma, providing feedback of the insertion (Choudhury et al., 2012, Dalbert et al., 2015b, Giardina et al., 2019, Fontenot et al., 2019).

Our first aim is to compare the hearing preservation in CI recipients with different combinations of surgical approach (CO and RW) and type of cochlear implant (LW and PM). Secondly, we want to investigate these treatment options by assessing the cone beam CT images postoperatively. Thirdly, we want to find ECochG outcome measures that reflect best the extent of insertion trauma by comparing these measures to the CT images and hearing test scores.

[figure not shown]

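### Section 7.1 tests ECochG measures only one at a time, which cannot show that one reflects insertion trauma better than another, as the third aim asks

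*Protocol*

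**What the plan says.** Section 1 sets the third aim: "we want to find ECochG outcome measures that reflect best the extent of insertion trauma by comparing these measures to the CT images", and it goes on to add hearing test scores as a second benchmark. Section 2 repeats it as a secondary objective: "To find which ECochG measures can be used best for assessment of insertion trauma". Section 2 also lists, as separate objectives, the relationship of ECochG measures with residual hearing and speech perception, and with scalar position.

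Section 5.3 gives the candidates: "Outcome measures include the CM amplitude and the total ECochG amplitude". It suggests a further one, since "the difference in the amplitude of the total ECochG response after and before insertion might contain information about insertion trauma". All are recorded in the same patients at the most apical contact, and the cochlear microphonic (CM) is described as one component of the ECochG response.

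Section 7.1 states one ECochG analysis: "We will use a Pearson correlation test to examine the correlations between the ECochG responses and hearing preservation at the various time points". It also plans a multiple regression for predictors of hearing preservation and says of it: "Among the factors to examine are insertion depth and cochlear volume". ECochG is not named there. No analysis compares one ECochG measure with another, and no rule is given for calling a measure best.

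**The concern.** Choosing among measures is a comparative question. Its null hypothesis is that two measures relate equally to hearing preservation (ρ1 = ρ2). A Pearson test has the null ρ = 0 for one measure alone. One significant and one non-significant result do not show that two measures differ, and ordering measures by observed r always puts one first, even when all are equally good.

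The candidates come from the same patients and overlapping signals, so their correlations with hearing preservation are dependent. Separate tests do not use that pairing. The third aim could therefore end by recommending a measure that is no better than the one set aside. It could also miss a real difference between closely related measures, where the pairing carries most of the information.

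**Working it through.** **The plan's own figure.** The Protocol gives no figure for the ECochG aim. Its one power statement is for the primary ANOVA, and it reproduces: f = 20/35 = 0.571, λ = 0.571² × 48 = 15.67, F on 3 and 44 df, alpha 0.05 (assumed), power 0.90. It matters here only because it fixes the sample size.

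**Inputs.**
- N = 48 (Summary; 4 groups of 12 in section 4.4).
- Two named measures (section 5.3).
- Assumed, because not in the Protocol: two-sided alpha 0.05; a true correlation of each measure with hearing preservation of 0.3, 0.4 or 0.5; a correlation between the two measures of 0.5, 0.7 or 0.9; multivariate normal data.

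**Step 1: what one Pearson test can see.** The critical value is r = t/√(n − 2 + t²) with t = 2.013 on 46 df, so r = 2.013/√(46 + 4.052) = 0.285. Observed correlations of 0.29 and 0.28 would fall on opposite sides of it, although they are practically the same.

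**Step 2: how often two equally good measures split.** P(split) = P(first significant) + P(second significant) − 2 × P(both significant). At true r = 0.3 and between-measure correlation 0.5, simulation gives 0.553 + 0.553 − 2 × 0.382 = 0.342. All settings (100,000 simulated trials each):

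| True r, both measures | Between-measure 0.5 | 0.7 | 0.9 |
|---|---|---|---|
| 0.3 | 34% | 26% | 15% |
| 0.4 | 22% | 17% | 10% |
| 0.5 | 6.5% | 5.4% | 3.4% |

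In the same data the median gap between the two observed correlations is 0.04 to 0.09, by chance alone.

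**Step 3: a direct comparison.** Williams' test for two correlations that share one variable:

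t = (r1 − r2) √{ (n − 1)(1 + r12) / [2K(n − 1)/(n − 3) + r̄²(1 − r12)³] }, on n − 3 = 45 df,

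with K = 1 − r1² − r2² − r12² + 2·r1·r2·r12 and r̄ the mean of r1 and r2.

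Example with observed r1 = 0.5, r2 = 0.3, r12 = 0.7: K = 1 − 0.25 − 0.09 − 0.49 + 0.21 = 0.38. The numerator is 47 × 1.7 = 79.9. The denominator is 2 × 0.38 × 47/45 + 0.16 × 0.027 = 0.798. So t = 0.2 × √(79.9/0.798) = 2.00, against a critical value of 2.014. Both correlations exceed 0.285, yet a gap of 0.2 falls just short of separating the measures.

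For the equal measures of step 2, Williams' test declares a difference in about 5% of trials in every cell, as it should.

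**Step 4: measures that truly differ (0.5 v 0.3).**

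| Between-measure correlation | Significance split | Williams' test |
|---|---|---|
| 0.5 | 42% | 33% |
| 0.7 | 41% | 50% |
| 0.9 | 41% | 95% |

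The split hardly changes with the pairing. The direct test gains from it. At 0.5 the split appears more sensitive, but it has no control over false separation: at the same between-measure correlation it separates equal measures in up to 34% of trials.

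**The case against.** The strongest reply is that the Pearson sentence is a suitable analysis for a different objective, the relationship between ECochG measures and residual hearing, and that nothing in section 7.1 offers it as the method for choosing among measures. That stands. It would be wrong to infer that the Protocol has picked an incorrect test.

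A reader might also infer that 'best' will be read from p-values or from the largest r. The Protocol says neither, so the split rates above describe a rule that could be adopted, not one that is stated. Nor does the text require a single winner: sections 1 and 2 speak of measures in the plural, and a shortlist would fit the wording.

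The regression in section 7.1 has an open list of factors and could take in ECochG measures. None is named, however, and coefficient p-values would not by themselves rank them.

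The size depends on assumed correlations. As CM is part of the ECochG response, a high between-measure correlation is plausible, and that points to the lower end of each range. If two measures really are equal, choosing either costs little; the harm is an overstated claim.

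It could also be said that the method for an exploratory aim belongs in a statistical analysis plan not shown here. That limits the weight of the point but does not remove it. The Protocol itself states the comparative aim and the analyses, and the one ECochG analysis it states cannot answer that aim.

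**Conclusion.** The point holds as an inexpensive improvement to a secondary aim. The analysis stated in section 7.1 describes each measure's association with hearing preservation; it gives no basis for saying that one measure is better than another. If significance were used to choose, equally good measures would be split in about 15% to 34% of trials at a true correlation of 0.3, 10% to 22% at 0.4 and 3% to 7% at 0.5, against about 5% declared different by a direct comparison. All of this rests on N = 48, an assumed alpha of 0.05 and an assumed between-measure correlation of 0.5 to 0.9. The problem is small under that rule once true correlations reach about 0.5; ordering by the largest r would still name a winner by chance. The primary comparison and its sample size are untouched.

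**What to change.** In section 7.1, keep the Pearson correlations and report each with a 95% confidence interval. For the ECochG measures named in section 5.3, taken at a common time point in the same patients, add the paired difference in their correlations with hearing preservation and its 95% interval, by a Williams/Steiger method for dependent correlations or a patient-level bootstrap. State that one measure will be called better than another only if that interval excludes zero, and that otherwise the measures will be reported as not separated. The alternative is to reword the objective in sections 1 and 2 as describing each measure's association.

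The cost is one or two sentences and a little analysis, with no extra patients, visits or data. There are two drawbacks. Power is modest: for true correlations of 0.5 and 0.3 it is about 33% to 50% at a between-measure correlation of 0.5 to 0.7, so the trial will often report that the measures could not be separated. And a comparison based on hearing preservation does not cover the CT benchmark that section 1 also names for this aim.
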